**\*Which IRB\***

The **Medical IRB** reviews research from the Colleges of:

- Dentistry
- Health Sciences
- Medicine
- Nursing
- Pharmacy and Health Sciences
- and Public Health.

The **Nonmedical IRB** reviews research from the Colleges of:

- Agriculture
- Arts and Sciences
- Business and Economics
- Communication and Information
- Design; Education
- Fine Arts
- Law
- and Social Work

**Note:** Studies that involve administration of drugs, testing safety or effectiveness of medical devices, or invasive medical procedures must be reviewed by the **Medical IRB** regardless of the college from which the application originates.

**\*Which Protocol Process Type\***

Under federal regulations, the IRB can process an application to conduct research involving human subjects in one of three ways:

- by exemption certification
- by expedited review.
- by full review;

The investigator makes the preliminary determination of the type of review for which a study is eligible. Please refer to ORI's "[Getting Started](#)" page for more information about which activities are eligible for each type of review.

The revised Common Rule expanded exemption certification category 4 for certain secondary research with identifiable information or biospecimens. The regulations no longer require the information or biospecimens to be existing. For more information see the [Exemption Categories Tool](#).

## EXPEDITED CERTIFICATION

0 unresolved  
comment(s)

## To Be Completed Only If Protocol is to Receive Expedited Review

## Applicability

- A. Research activities that (1) present no more than \*minimal risk to human subjects, and (2) involve only procedures listed in one or more of the following categories, may be reviewed by the IRB through the expedited review procedure authorized by 45 CFR 46.110 and 21 CFR 56.110. The activities listed should not be deemed to be of minimal risk simply because they are included on this list. Inclusion on this list merely means that the activity is eligible for review through the expedited review procedure when the specific circumstances of the proposed research involve no more than minimal risk to human subjects.
- B. The categories in this list apply regardless of the age of subjects, except as noted.
- C. The expedited review procedure may not be used where identification of the subjects and/or their responses would reasonably place them at risk of criminal or civil liability or be damaging to the subjects' financial standing, employability, insurability, reputation, or be stigmatizing, unless reasonable and appropriate protections will be implemented so that risks related to invasion of privacy and breach of confidentiality are no greater than minimal.
- D. The expedited review procedure may not be used for classified research involving human subjects.
- E. IRBs are reminded that the standard requirements for informed consent (or its waiver, alteration, or exception) apply regardless of the type of review—expedited or convened—utilized by the IRB.

*\*“Minimal risk” means that the probability and magnitude of harm or discomfort anticipated in the research are not greater in and of themselves from those ordinarily encountered in daily life or during the performance of routine physical or psychological examination or tests. 45 CFR 46.102(i)*

Check the appropriate categories that apply to your research project:

- Study was originally approved by the full IRB at a convened meeting.
- 1) Clinical studies of drugs and medical devices only when condition (a) or (b) is met.
  - A. Research on drugs for which an investigational new drug application is not required. (Note: Research on marketed drugs that significantly increases the risks or decreases the acceptability of the risks associated with the use of the product is not eligible for expedited review.)
  - B. Research on medical devices for which (i) an investigational device exemption application is not required\*; or (ii) the medical device is cleared/approved for marketing and the medical device is being used in accordance with its cleared/approved labeling.\*\*

\* Study must meet one of the IDE Exempt categories listed on the Device Form Attachment.

\*\* An approved Device used in research according to its approved labeling is considered Exempt from IDE requirements.

NOTE: Select Category 1 for compassionate use medical device applications or individual patient expanded access investigational drug applications for which FDA has waived the requirement for full review.

2) Collection of blood samples by finger stick, heel stick, ear stick, or venipuncture as follows:

- A. From healthy, nonpregnant adults who weigh at least 110 pounds. For these subjects, the amounts drawn may not exceed 550 ml in an 8 week period and collection may not occur more frequently than 2 times per week; or
- B. From other adults and children\* considering the age, weight, and health of the subjects, the collection procedure, the amount of blood to be collected, and the frequency with which it will be collected. For these subjects, the amount drawn may not exceed the lesser of 50 ml or 3 ml per kg in an 8 week period and collection may not occur more frequently than 2 times per week.

NOTE: Intravenous (IV), Port, Central, or any other lines are NOT eligible under this category even if the research involves “minimal risk”.

\*In Kentucky, “child/children” refers to all individuals less than 18 years of age unless the individual(s) is/are legally emancipated. (See [Informed Consent SOP](#) for discussion of “Emancipated Individuals” under Kentucky state law.) Individuals less than 18 years of age who are not emancipated meet the federal definition for “child” (e.g., DHHS, FDA, and U.S. Department of Education). Children are defined in the HHS regulations as “persons who have not attained the legal age for consent to treatments or procedures involved in the research, under the applicable law of the jurisdiction in which the research will be conducted.” If conducting research outside the state of Kentucky, you are responsible for complying with applicable state law.

3) Prospective collection of biological specimens for research purposes by noninvasive means. Examples:

- A. Hair and nail clippings in a nondisfiguring manner;
- B. Deciduous teeth at time of exfoliation or if routine patient care indicates a need for extraction;
- C. Permanent teeth if routine patient care indicates a need for extraction;
- D. Excreta and external secretions (including sweat);
- E. Uncannulated saliva collected either in an unstimulated fashion or stimulated by chewing gumbase or wax or by applying a dilute citric solution to the tongue;
- F. Placenta removed at delivery;
- G. Amniotic fluid obtained at the time of rupture of the membrane prior to or during labor;
- H. Supra- and subgingival dental plaque and calculus, provided the collection procedure is not more invasive than routine prophylactic scaling of the teeth and the process is accomplished in accordance with accepted prophylactic techniques;
- I. Mucosal and skin cells collected by buccal scraping or swab, skin swab, or mouth washings;
- J. Sputum collected after saline mist nebulization.

4) Collection of data through noninvasive procedures (not involving general anesthesia or sedation) routinely employed in clinical practice, excluding procedures involving x-rays or microwaves. Where medical devices are employed, they must be cleared/approved for marketing. (Studies intended to evaluate the safety and effectiveness of the medical device are not generally eligible for expedited review, including studies of cleared medical devices for new indications.) Examples:

- A. Physical sensors that are applied either to the surface of the body or at a distance and do not involve input of significant amounts of energy into the subject or an invasion of the subject's privacy;
- B. Weighing or testing sensory acuity;
- C. Magnetic resonance imaging;
- D. electrocardiography, electroencephalography, thermography, detection of naturally occurring radioactivity, electroretinography, ultrasound, diagnostic infrared imaging, doppler blood flow, and echocardiography;
- E. moderate exercise, muscular strength testing, body composition assessment, and flexibility testing where appropriate given the age, weight, and health of the individual.

5) Research involving materials (data, documents, records, or specimens) that have been or will be collected solely for non-research purposes (such as medical treatment or diagnosis) as well as research involving existing information or specimens that were previously collected for research purposes, provided they were not collected for the currently proposed research. (Note: Some research in this category may qualify for Exempt review. This listing refers only to research that is not exempt.)

(Note: If submission includes materials previously collected for either non-research or research purposes in a protocol for which IRB approval expired, you may check Category 5. However, a separate category must also be selected for prospective collection of data/specimens obtained solely for research purposes)

6) Collection of data from voice, video, digital, or image recordings made for research purposes.

7) Research on individual or group characteristics or behavior (including, but not limited to, research on perception, cognition, motivation, identity, language, communication, cultural beliefs or practices, and social behavior) or research employing survey, interview, oral history, focus group, program evaluation, human factors evaluation, or quality assurance methodologies. (Note: Some research in this category may be exempt from the HHS regulations for the protection of human subjects. This listing refers only to research that is not exempt.)

## PROJECT INFORMATION

**0 unresolved  
comment(s)**

Title of Project: (Use the exact title listed in the grant/contract application, if applicable).

If your research investigates any aspect of COVID-19, please include "COVID19" at the beginning of your Project Title and Short Title

COVID19 Kentucky Communities and Researchers  
Engaging to Halt the Opioid Epidemic (CARE2HOPE) -  
UH3 PHASE

**Short Title Description**

Please use a few key words to easily identify your study - this text will be displayed in the Dashboard listing for your study.

COVID19 CARE2HOPE UH3

Anticipated Ending Date of Research Project: Maximum number of human subjects (or records/specimens to be reviewed) After approval, will the study be open to enrollment of new subjects or new data/specimen collection?  Yes  No

**RISK LEVEL****0 unresolved  
comment(s)**

Indicate which of the categories listed below accurately describes this protocol

- (Risk Level 1) Not greater than minimal risk
- (Risk Level 2) Greater than minimal risk, but presenting the prospect of direct benefit to individual subjects
- (Risk Level 3) Greater than minimal risk, no prospect of direct benefit to individual subjects, but likely to yield generalizable knowledge about the subject's disorder or condition.
- (Risk Level 4) Research not otherwise approvable which presents an opportunity to understand, prevent, or alleviate a serious problem affecting the health or welfare of subjects.

\*\*"Minimal risk" means that the probability and magnitude of harm or discomfort anticipated in the research are not greater in and of themselves from those ordinarily encountered in daily life or during the performance of routine physical or psychological examination or tests.

**\*\*\*For Expedited and Exempt Applications, the research activities must be Risk Level 1 (no more than minimal risk to human subjects).\*\*\***

Refer to [UK's guidance document](#) on assessing the research risk for additional information.

**SUBJECT DEMOGRAPHICS****0 unresolved comment(s)**

Age level of human subjects: (i.e., 6 mths.; 2yrs., etc.)  to

**Study Population:**

Describe the characteristics of the subject population, including age range, gender, ethnic background and health status. Identify the criteria for inclusion and exclusion.

Provide the following information:

- A description of the subject selection criteria and rationale for selection in terms of the scientific objectives and proposed study design;
- A compelling rationale for proposed exclusion of any sex/gender or racial/ethnic group;
- Justification for the inclusion of vulnerable groups such as children, prisoners, adults with impaired consent capacity, or others who may be vulnerable to coercion or undue influence.

Please consider these resources:

[NIH Diversity Policy](#)

[FDA Diversity Guidance](#) 

CARE2HOPE covers the following counties: Rowan, Bath, Morgan, Menifee, Elliott, Lee, Owsley, Wolfe, Perry, Letcher, Leslie, Knott. We will recruit participants at all seven jails serving the 12 CARE2HOPE counties; these jails are either located in our CARE2HOPE counties (N=5; Rowan, Lee, Perry, Leslie, Letcher), or our counties have contracts with them to incarcerate their residents (N=2; Montgomery, Clark). To be eligible to take part in Project START-C2H, an individual must:

EITHER:

- (1) be a participant in the CARE2HOPE longitudinal survey (IRB Protocol #43520) who consented to be contacted for future research; and
- (2) be a resident of or anticipate being released to one of the 12 CARE2HOPE counties randomized to intervention or control data collection; and
- (3) be incarcerated in a local jail and expected to be released in <21 days;

OR:

- (1) Be a resident of or anticipate being released to one of the 12 CARE2HOPE counties randomized to intervention or control data collection
- (2) Have used opioids to get high in the 30 days before they were incarcerated, or have injected any drug to get high during that period;
- (3) Be aged 18 or older
- (4) be incarcerated in a local jail and expected to be released in <21 days

We have the opportunity to offer the intervention to individuals enrolled in the comparison counties who have completed 3-month surveys, and feel that offering them this intervention is an ethical best practice. We are not proposing any additional quantitative data collection with them, but these individuals will be eligible for qualitative interviews as part of our continuous quality improvement component.

Exclusion criteria are: (1) not speaking English fluently; (2) residence in or move to a county not randomized to intervention or control data collection within 21 days of release; (3) transfer to prison; (4) having ever been convicted of or currently being charged with a violent crime (e.g., homicide, murder, rape and sexual assault, robbery, and/or felony assault); and (5) having been incarcerated for one year or more.

We anticipate that we will recruit 1200 individuals into the study (600 in the comparison group and 600 in the intervention group). The vast majority will be non-Hispanic [name], aligned with the racial/ethnic composition of the area; slightly more than half will be men.

**COVID-19 Policies**

We are expanding the eligibility criteria to include individuals in community settings who report recent criminal justice involvement. To be eligible to take part in Project START-C2H, an individual must:

- (1) Be aged 18 or older; and
- (2) A resident of one of the 12 CARE2HOPE counties randomized to intervention or control data collection; and
- (3) Have used opioids or have injected any drug to get high during the past 30 days (if incarcerated, on an ankle monitoring home incarceration program, out on bond, under warrant for arrest, arrested, court-involved, on pre-trial supervision, probation or parole, or enrolled in a substance use disorder treatment program, eligible if injected drugs or used opioids to get high in the 30 days before this particular involvement with the criminal justice system or substance use disorder treatment program); and
- (4) Have been recently involved in the criminal justice system defined as being incarcerated in jail or prison, out on bond, under warrant for arrest, arrested, under pre-trial supervision, on probation or parole, court-involved, or incarcerated at home under an electronic monitoring program (i.e., digital jail) in the past 30 days.

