#### COVID-19 Policies

We are changing the trial duration from three years to two years. To accommodate this shorter time period, we are modifying the study design from a stepped-wedge trial to a case crossover trial. We will randomize the 12 counties to two groups of six counties each versus three groups of four counties each. All counties will start at the same time. During months 1-6, counties randomized into Group 1 will receive the intervention, while counties randomized to Group 2 will serve as the comparison group. In Months 7-12, Group 1 counties will shift to the comparison group, and Group 2 counties will receive the intervention. In Months 13-18 we will conduct follow-up assessments in all counties. Months 19-24 will be devoted to data analysis and dissemination of the findings.

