#### Comparison Condition

We will initiate the comparison group in each county six months before the intervention begins. The current "treatment as usual" condition for most individuals, especially individuals not entering parole/probation supervision, is to provide no post-release services. Given the high risk of overdose post-release, we will conduct a pre-release overdose intervention with the comparison cohort. Individuals recruited in the community will receive overdose education during their baseline visit as well. Overdoses are not a primary study outcome, and it would be unethical to withhold overdose education from this cohort. Six months before the intervention starts in a county, REHNS will use the same pre-release recruitment, consent, and enrollment protocols (including eligibility criteria, except individuals must live in counties that are currently randomized to the comparison group) as proposed for the intervention condition. As with START's original evaluation, we will administer a single session, pre-release intervention for the comparison group; if someone is recruited in the community, they will receive this visit as well. Specifically, the comparison group participants will complete the a training with people demonstrating how to respond to an overdose and narration on preventing, recognizing, and responding effectively to an opioid OD, accompanied by information about Kentucky's Good Samaritan Law and Naloxone Access Law. REHNS will answer questions after the video. Individuals will receive a Community Resource Guide at this visit.

As in the intervention group, comparison group participants will complete assessments at pre-release (two sessions), for those recruited in the community this will happen at the REHNS office, and at 3 months and 6 months weeks post-release (post-enrollment for those recruited in the community). Surveys will be identical to those delivered to the intervention cohort, as will incentives. No interventions will be delivered at these follow up appointments. Retention efforts for comparison participants will be identical to those for intervention participants (described previously).

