Survey content: Prospective participants will complete a screening survey (described above, see Screening Survey attached) to determine eligibility. Surveys (see START-C2H Survey appendix) will capture the following domains: (1) sociodemographic characteristics; (2) all possible behavioral targets; and (3) health and social service engagement. The survey will closely resemble that

used in the currently approved CARE2HOPE study under IRB protocol #43520. Of note, the survey instructions will clearly indicate that time periods at baseline refer to time before incarceration and, when repeated for follow-up visits, recall periods will be adjusted accordingly (i.e., language referring to lifetime or past 6 month behavior will be changed to past 3 months). Surveys will take 45-60 minutes to complete (survey administration methods are described above).

Drug screening: We will conduct Urine or saliva drug Screens at the 1-week, 3-month, and 6-month appointments. We will not conduct drug screening in the jail. As in CARE2HOPE UG3 phase (Protocol #43520), we will use HomeHealth's iCup Drug Test that tests for 13 drugs including opiates (heroin and morphine), buprenorphine, methadone, oxycodone, as well as various stimulants, sedatives, and other drugs. For saliva test, we will use SalivaConfirm (TestCountry, San Diego, CA) drug screening kit that detects 10 types of illicit drugs in the sample in 10 minutes.

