### Exploratory Quantitative Analysis of START-C2H survey data:

Our community randomized trial consists of clustered data with participants nested within counties. To account for this "doubly-repeated" measures design, we will analyze all results using generalized linear mixed models. The covariance matrix for all observations within a county may be written as the Kronecker product of the compound symmetric covariance matrix for participants nested within county and a 2 by 2 residual covariance matrix for repeated measures nested within participants. Implementing the covariance model can be done in both PROC MIXED (for continuous measures) and PROC GLIMMIX (for categorical measures) in SAS by specifying a random intercept for county, and a compound symmetric residual matrix across time (repeated measures within participant). To estimate change in our primary outcomes due to the intervention we will begin by analyzing models of the following form:  $g(y) = \beta_0 + \beta_1 Time + \beta_2 Int + \beta_3 Time * Int$  where  $g()$  represents the appropriate link function for outcome  $y$ ,  $Time$  is a pre-post indicator variable, and  $Int$  is an indicator for the intervention group. The parameter of primary interest is  $\beta_3$ , the difference in slope between the intervention and control group. While our primary outcomes can be approximated as normally distributed, the link function  $g()$  will be modified as necessary to properly model the distribution for each outcome.

**Missing Data.** We will use multiple imputation to account for non-response over time and potential attrition. Additional augmentation variables found to be predictive of missingness will also be included in the imputation model. Ten imputations will be implemented. Additionally, we will use multiple imputation by chained equations to allow for imputation of non-normally distributed variables. All imputation analyses will be done using PROC MI and PROC MIANALYZE in SAS.

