**Power.** We estimated the statistical power to preliminarily detect a change in our outcomes using PROC GLMPOWER in SAS v9.4., accounting for autocorrelation within participants and nesting within counties. We estimate power for a multivariate model equivalent to our planned repeated measures models previously described. Because these analyses are exploratory (due to the smaller-than-anticipated sample size), we set the alpha to 0.10. Based on existing data, we assume a within-county ICC of 0.05 and a within-person autocorrelation of 0.35. We estimate power for all outcomes as approximately Gaussian. We further assume a type-1 error rate of 0.10, 12 counties, and 20 participants per county. At these sample sizes and with an exploratory p-value=0.10, we achieve statistical power of 0.80 for standardized mean of 0.55, or moderate sized effects with an alpha=0.10.

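### Jail and community recruits have different time zeros but share one pre-post model with no recruitment-setting term, so any jail-share difference left between arms can bias Time*Int

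*Combined protocol and SAP*

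**What the plan says.** The trial began with recruitment in jails. The COVID-19 text under Study Population adds a second route: "We are expanding the eligibility criteria to include individuals in community settings who report recent criminal justice involvement".

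The two routes are measured differently.

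- **Time zero.** Comparison Condition and the survey-administration text in Data Collection & Research Materials time the 3- and 6-month assessments from release for jail recruits and "post-enrollment for those recruited in the community".
- **Survey baseline.** Data Collection & Research Materials says that "time periods at baseline refer to time before incarceration", with recall periods changed at follow-up. It gives no equivalent window for community recruits.
- **Drug screen.** None is done in jail, and the schedule starts at the 1-week appointment. CARE2HOPE's enhancements to START places the community recruits' screen with their baseline, before the first intervention visit.

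The Exploratory Quantitative Analysis section analyses everyone together. Time "is a pre-post indicator variable", and the other fixed terms are Int and Time*Int. The random part is a county intercept plus a within-person residual matrix. No setting term, stratification or sensitivity analysis by setting appears. Additional variables are mentioned only for the imputation model.

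On allocation, the COVID-19 text under Study Design says "We will randomize the 12 counties to two groups of six counties each versus three groups of four counties each". All counties start together and the two groups exchange conditions at month 7.

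**The concern.** For a jail recruit, the change runs from use before incarceration, across a period in custody, to use after release. For a community recruit it runs from a baseline taken in the community to a point counted from enrollment. These two changes need not have the same expected value in the absence of any intervention. A single Time indicator treats them as the same quantity.

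If the arms then hold different proportions of jail recruits, part of the difference in change between arms reflects route of recruitment and not the intervention. That part falls on Time*Int, the coefficient of primary interest. The triangulation section uses results at p < 0.10 from these models to conclude benefit, harm or no effect, so a shift in this coefficient could alter a conclusion even though the analysis is labelled exploratory.

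**Working it through.** **1. Reproduce the plan's power.** The inputs come from the Power paragraph: "we assume a within-county ICC of 0.05 and a within-person autocorrelation of 0.35"; "We further assume a type-1 error rate of 0.10, 12 counties, and 20 participants per county"; "we achieve statistical power of 0.80 for standardized mean of 0.55". I assume a two-sided test, two parallel groups of six counties (120 people per arm) and 12 - 2 = 10 degrees of freedom. The plan does not state these.

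- Variance of a pre-post change: 2(1 - 0.35) = 1.30 SD².
- Design effect: 1 + (20 - 1) x 0.05 = 1.95.
- SE of the difference in change: sqrt(1.30 x 1.95 x 2/120) = 0.2055 SD.
- Power at 0.55, noncentral t on 10 df, alpha 0.10: 0.8006.

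This matches the stated 0.80, so the question is bias and not the power figure.

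**2. Form of the bias.** Let p be the jail share in an arm and g the jail-minus-community difference in mean change, the same in both arms. Mean change is b1 + g x p(control) in the control arm and b1 + b3 + g x p(intervention) in the intervention arm, where b1 is the mean change of community controls. Subtracting gives

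expected Time*Int = b3 + g x [p(intervention) - p(control)].

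Both factors must be non-zero. Simulation with a true effect of 0 agrees:

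- share difference 0.3 and g = 0.5 SD: estimate 0.149;
- share difference 0: estimate -0.001;
- baseline level 0.5 SD apart but g = 0: estimate 0.000.

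A difference in level alone cancels. Only a difference in change matters.

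**3. Size.** The documents give neither factor. The values below are assumptions; rejection rates use the SE and 10 df from step 1.

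| Share difference | g (SD) | Bias (SD) | % of 0.55 | Type I error (nominal 0.10) | Power at 0.55 if bias opposes it |
|---|---|---|---|---|---|
| 0.1 | 0.3 | 0.03 | 5% | 0.103 | 0.761 |
| 0.1 | 0.5 | 0.05 | 9% | 0.109 | 0.732 |
| 0.2 | 0.5 | 0.10 | 18% | 0.135 | 0.653 |
| 0.3 | 0.5 | 0.15 | 27% | 0.178 | 0.567 |

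**4. Can the share differ under the crossover?** If jail share were only a county effect plus a period effect, with equal enrollment, its expected arm difference would be zero. What remains is variation within a county between periods. As an illustration, if that residual had an SD of 0.3, the arm difference over 12 counties would have an SD of 0.3 x sqrt(2/12) = 0.12. A difference near 0.1 is then unremarkable. One of 0.3 is about 2.4 SDs out (0.3/0.1225 = 2.45) and would more likely need a systematic cause.

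**5. Effect of the remedy.** With Setting*Time in the model, the simulated estimate is within 0.002 of the true value of 0. With half the sample from jail and equal arms, the variance inflation is 1/(1 - d²) for share difference d.

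| d | Inflation | SE | Power at 0.55 |
|---|---|---|---|
| 0 | 1.000 | 0.2055 | 0.801 |
| 0.1 | 1.010 | 0.2066 | 0.797 |
| 0.2 | 1.042 | 0.2098 | 0.786 |
| 0.3 | 1.099 | 0.2155 | 0.767 |

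The residual SD is held fixed, so any variance that the term explains is not credited.

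**The case against.** The strongest reply is the crossover. Every county serves in both conditions and every period contains both arms, so lasting county differences in jail access and trial-wide shifts in COVID restrictions largely cancel. This stands. A reader might infer that the recruitment mix is left wholly unbalanced by the design, and the Study Design text does not support that. The crossover does not remove three sources: jail access that changes in some counties between periods, recruitment of individuals after the county's condition is known, and the early enrollees. On the last, the text on recruitment from existing cohorts says that four counties began as controls in November 2019 under the stepped-wedge design, which recruited in jails. They were later assigned to intervention and their enrollees made eligible for it. The documents do not say whether those people enter the analysis.

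Other points also stand.

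- A reader might take community baselines to describe recent behaviour at liberty. The community recall window is not stated. The eligibility text also lets many community recruits qualify on drug use in the 30 days before their justice or treatment involvement.
- A reader might suppose that the 15-person recruitment hold fills from whichever route is quickest. The text says only that recruitment pauses and resumes at the switch.
- Different time zeros are not an error in themselves. In the intervention arm they line follow-up up with the start of community contact. The difficulty lies in pooling them under one Time term.
- The split between routes is not clean. Some jail recruits may complete baseline sessions after release, and some community recruits were recently in jail.
- The model is described as a starting form within an exploratory analysis, so a setting term is not ruled out. None is pre-specified, however, and a term chosen after seeing the data carries less weight.

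The plan's remark that it is underpowered for effect moderation does not answer the point. Setting*Time adjusts for a confounder; only a three-way term with Int would be moderation.

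**Conclusion.** The concern holds as a conditional weakness of the model. The two routes have different time zeros, jail recruits have a pre-incarceration survey baseline, and the specified terms cannot separate route from intervention if the jail share differs between arms after the crossover has done its work.

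Under the assumed ranges the bias is 0.03 to 0.15 SD. That is 5% to 27% of the 0.55 SD used for power, and below one standard error (0.2055) throughout. At the low end it hardly matters. At the high end, type I error rises from 0.10 to about 0.18. A reader might conclude that the estimate will be biased by some such amount. The documents do not support that, because they report neither the jail share by arm nor the change by setting, and if either difference is zero so is the bias. Confidence is medium.

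**What to change.** Before the outcome data are analysed, add recruitment setting (jail or community) and Setting*Time as fixed effects to the model in the Exploratory Quantitative Analysis section, and put both in the imputation model. A setting main effect alone would not remove the bias, because it adjusts the level and not the change. Report the setting mix by arm and period, so that readers can see whether an imbalance arose. Define setting as the route at enrollment, which deals with people whose baseline sessions straddle release. State whether the early enrollees in the four counties are analysed and, if so, in which arm.

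This is cheap but not free. It uses two model parameters. Power at 0.55 moves from 0.80 to about 0.797, 0.786 or 0.767 at share differences of 0.1, 0.2 or 0.3, under the assumptions in the working. Setting must also be derived from enrollment records. Procedures and payments already differ by route, so this should be feasible, but the documents do not say that it is held as an analysis variable.
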